## 9 SAFETY ANALYSIS

All Safety analyses will be conducted using the Safety population.

### 9.1 Adverse events

Adverse events are defined in protocol Section 7.2. As the definition includes only events which occur after first study-drug administration, all AEs are considered to be ‘treatment emergent’. Pre-treatment events are reported as medical history. Relationship and action taken referring to ampicillin and aminoglycoside are listed only.

An overview summary of number and percentage of patients will be provided for any AE, study-drug-related AEs, SAEs, study-drug-related SAEs, AEs leading to treatment discontinuation, study-drug-related AEs leading to treatment discontinuation, AEs leading to treatment interruption / dose reduction, study-drug-related AEs leading to treatment interruption / dose reduction, AEs leading to death, study-drug-related AEs leading to death, AEs of special interest (see Section 9.1.4), and study-drug-related AEs of special interest will be provided.

All AEs, SAEs, and AEs leading to death will be presented in separate listings.

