## 7.2 Definitions

### 7.2.1 Adverse event

An AE is defined as any untoward medical occurrence in a patient or clinical investigational patient administered a pharmaceutical product that does not necessarily

have a causal relationship with study-drug treatment. An AE can therefore be any unfavourable and unintended sign (for example, including an abnormal laboratory finding), symptom, or disease temporally associated with the use of a medicinal product, whether or not considered related to the medicinal product. Complications associated with scheduled procedures are considered AEs.

Events that occur following the full execution of the ICF but prior to dosing are discussed in Section [7.4.2](#).

Adverse events will be coded using the standard Medical Dictionary for Regulatory Activities (MedDRA), and grouped by System Organ Class and Preferred Term.

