#### **7.4.2 Handling of safety data during the pre-treatment period**

Any relevant change in, or worsening of, a patient's condition occurring after execution of the study ICF but prior to dosing, is to be recorded in the medical history page of the eCRF (see Section 5.3.1), unless the occurrence is assessed as related to the study procedure, in which case it must be recorded in the AE page. If the event is assessed as both serious (see Section 7.2.2) and related to study-specific procedures, it must be reported to the Sponsor's safety representative, using the same procedures as for an SAE (see Section 7.4.3.2).

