### 9.1.1 Incidence of adverse events

The number and percentage of patients reporting AEs will be tabulated by SOC and PT for all AEs, and separately for study-drug-related AEs. Patients with multiple events will be counted only once within each category. SOC and PT will be sorted in descending order of frequency in the total of all treatment groups.

In addition, the following categories will be summarized similarly:

- AEs up to EOT visit
- AEs up to TOC visit
- SAEs
- AEs leading to treatment discontinuation
- AEs leading to treatment interruption / dose reduction.

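### SAP 9.1 treats every AE as treatment emergent and misses the exception in protocol 7.4.2 that puts pre-dose, procedure-related events on the AE page; with no onset condition, such events would enter the safety tables.

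*SAP*

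**What the plan says.** SAP 9.1 refers to protocol 7.2 for the definition of an AE and draws a conclusion from it: "As the definition includes only events which occur after first study-drug administration, all AEs are considered to be" treatment emergent. The next sentence reads: "Pre-treatment events are reported as medical history". It names no exception.

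Protocol 7.2.1 opens: "An AE is defined as any untoward medical occurrence in a patient or clinical investigational patient administered a pharmaceutical product that does not necessarily" (the sentence goes on to make causality no requirement). It also says: "Complications associated with scheduled procedures are considered AEs", with no time limit. For the interval before dosing it gives a pointer: "Events that occur following the full execution of the ICF but prior to dosing are discussed in Section" 7.4.2.

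Protocol 7.4.2 sends a relevant change between consent and dosing to the medical history page, "unless the occurrence is assessed as related to the study procedure, in which case it must be recorded in the AE page". Where such an event is also serious, it goes to the sponsor by the same route as an SAE.

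SAP 9.1.1 then specifies the main table: "The number and percentage of patients reporting AEs will be tabulated by SOC and PT for all AEs, and separately for study-drug-related AEs". The SAE summary is built in the same way, and SAP 9.1.4 summarises AESIs by SOC and PT. SAP 12 declares no changes from the protocol-defined analyses.

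**The concern.** The SAP needs no treatment-emergent flag if its premise holds, and it defines none. The premise fails for one class of record: an event related to a study procedure that occurs after consent and before the first infusion. The protocol deliberately places that record on the AE page, which is the source for the SAP's AE tables.

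AE incidence is part of the primary endpoint. As worded in SAP 3.2.1, that endpoint concerns AEs during treatment with ceftobiprole and at the EOT, TOC and LFU visits. An event before any exposure lies outside it, yet would appear in the tables as having arisen on treatment. With eight infants planned, a single record can visibly change a percentage.

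**Working it through.** There is no stated figure to reproduce beyond the sample size, 2 term + 6 pre-term = 8, which agrees. The check is mainly a comparison of texts.

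**Step 1: where does a pre-dose event go?**

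| Event after consent, before first dose | Protocol 7.4.2 | SAP 9.1 |
|---|---|---|
| Not related to study procedure | Medical history page | Medical history |
| Related to study procedure | AE page | Medical history |
| Related to study procedure and serious | AE page, plus SAE reporting | Medical history |

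The documents agree on the first row and disagree on the other two.

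**Step 2: does anything later in the SAP remove these records?**

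- SAP 9.1.1 tabulates all AEs and all SAEs without an onset condition.
- The summaries up to EOT and up to TOC have an upper time limit but no lower one.
- SAP 9.1.4 selects AESIs by MedDRA query or Preferred Term, not by date.
- No rule moves an AE-page record to medical history.

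The only restriction is the Safety population (SAP 4.2.1): infants who are never dosed drop out.

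**Step 3: effect of one record.** SAP 9.1.1 counts a patient once per category. If the pre-dose event is the infant's only event in a row, the row rises by 100/n percentage points:

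- overall: 100/8 = 12.5
- pre-term: 100/6 = 16.7
- term: 100/2 = 50.0

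If the infant has another event in the row, the rise is 0. The figures above are therefore maxima per infant. They fit rows for a specific term, SAE or AESI better than the row for any AE. The group sizes are planned minima; larger groups give smaller shifts.

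**Step 4: how likely is at least one case?** The documents give no rate, so the per-infant rate p is an assumption. With independent infants, P(at least one of 8) = 1 − (1 − p)^8:

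| Assumed p | P(at least one) | Expected number (8p) |
|---|---|---|
| 1% | 7.7% | 0.08 |
| 5% | 33.7% | 0.4 |
| 10% | 57.0% | 0.8 |
| 20% | 83.2% | 1.6 |

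The window and pre-dose procedures described in the protocol make the lower part of this range more plausible.

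**Step 5: would a simple date filter suffice?** Not fully, for two reasons.

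- Screening runs from Day −2 to Day 1, while protocol 7.4.3.1 asks only for AE start and end dates and SAP 4.3.5 treats time as optional. A date cannot separate events before and after the infusion on Day 1.
- SAP Appendix 1 sets an AE start date to the first-dose date when the day is missing and month and year match the first dose, when day and month are missing and the year matches, or when the date is wholly missing. A pre-dose event with such a date would pass a date filter.

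**The case against.** The strongest reply is that the SAP reads the protocol correctly in general. Protocol 7.2.1 speaks of a patient given a product and of events linked in time to its use. Protocol 7.4.3 starts AE collection at first dosing. Protocol 5.3.1 puts worsening between consent and first dose in medical history, 5.5.2 ties reportable physical changes to the period after first administration, and Table 3 schedules no AE assessment at screening. All this stands. A reader might infer that the SAP's premise is simply false, or that the AE definition has no link to dosing; the documents do not support that. The defect is the overlooked exception in 7.4.2, which is explicit and which 7.2.1 itself points to.

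Second, the medical-history sentence in SAP 9.1 shows an intent to keep pre-dose events out, and an analyst could act on it. This also stands, so one cannot say that the SAP directs these events to be counted. But the sentence describes where records are supposed to be; it is no rule for records that the protocol has placed on the AE page.

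Third, the affected set is small. The event must be related to a study procedure, fall in a short window, and occur in an infant who is later dosed. Recent screening laboratory tests need not be repeated, pre-dose microbiology and urine output depend on clinical indication, and PK sampling is on Day 3. All AEs are also listed, so with about eight infants each record can be inspected. This limits the practical weight of the point but does not settle which number the table should show.

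Finally, a reader might infer that drug-related AE counts are inflated too. That would require causality rated possible or probable, or left missing (SAP 4.3.4 then counts it as related). SAP 9.1.2 offers a not-applicable category that fits a pre-dose event, so this does not follow in general.

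**Conclusion.** The point holds as a conflict between SAP 9.1 and protocol 7.4.2, with no onset condition in the SAP to resolve it. As written, a study-procedure-related event before first dose in an infant who is later dosed would be counted as treatment emergent in the AE tables. It would also enter the SAE tables if serious, and the AESI tables if it matches one of the listed queries or terms.

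The increase is at most 12.5 points overall, 16.7 in pre-term or 50 in term per affected infant and row. This assumes the planned minimum sizes and no other event for that infant in that row. It would be wrong to read these as the effect of every such case. How often a case would arise cannot be derived from the documents; it is probably rare.

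The study is descriptive and no test is affected. The correction is still worth making before database lock, because it concerns a stated rule for the primary endpoint and the denominators are very small.

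**What to change.** In SAP 9.1, replace the sentence that makes all AEs treatment emergent, and the one after it, with the following provisions:

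1. An AE is treatment emergent if its onset or worsening is at or after the start of the first ceftobiprole infusion.
2. The AE, SAE and AESI tables use this flag.
3. AE-page records with pre-dose onset that are related to a study procedure (protocol 7.4.2) are listed separately, with seriousness shown; other pre-dose events remain medical history.
4. For events on Day 1, the flag uses onset time or a pre/post-dose indicator. Exact infusion start times are already recorded under protocol 5.2.2.
5. Events known to be pre-dose are exempt from the Appendix 1 imputation to the first-dose date.

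The cost is SAP wording, one derived flag and one short listing, plus possibly one eCRF indicator or a query for Day 1 events. No protocol change is needed.

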### 9.1.1 Incidence of adverse events

The number and percentage of patients reporting AEs will be tabulated by SOC and PT for all AEs, and separately for study-drug-related AEs. Patients with multiple events will be counted only once within each category. SOC and PT will be sorted in descending order of frequency in the total of all treatment groups.

In addition, the following categories will be summarized similarly:

- AEs up to EOT visit
- AEs up to TOC visit
- SAEs
- AEs leading to treatment discontinuation
- AEs leading to treatment interruption / dose reduction.

### 9.1.2 Relationship of adverse events to study drug

The relationship to ceftobiprole is collected based on the possibility that the study drug caused the event. The possible relationships are 'Not Related', 'Unlikely', 'Possible', 'Probable', and 'Not Applicable', with AEs assessed as 'Possible' or 'Probable' classified as study-drug-related.

A summary of AEs will also be presented by relationship to study drug, SOC and PT. If a patient reports multiple occurrences of the same AE, only the worst relationship category will be counted.

Adverse events that are missing an assessment of relationship to study drug will be counted in the study-drug-related AEs summary table, but will be presented in the summary table by relationship and in listing with a 'Missing' relationship.

### 9.1.3 Severity of adverse event

Severity of AEs is collected in the eCRF as 'Mild', 'Moderate', or 'Severe', and a summary of AEs by severity will be presented in a table. If a patient reports multiple occurrences of the same AE, only the most severe will be counted. AEs that are missing severity will be presented in tables as severity 'Unknown'.

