## 7.3 Evaluation of adverse events

### 7.3.1 Grading of severity

The severity of an AE will be graded on the following scale:

- Mild: no change in baseline age appropriate behaviour\*
- Moderate: resulting in minor changes of baseline age-appropriate behaviour
- Severe: resulting in major changes of baseline age-appropriate behaviour\* and/or non-life threatening changes in basal physiological processes\*\*
- Life-threatening
- Fatal

\* Age-appropriate behaviour refers to oral feeding behaviour, voluntary movements and activity, crying pattern, social interactions and perception of pain

\*\* Basal physiological processes refer to oxygenation, ventilation, tissue perfusion, metabolic stability and organ functioning

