### **8.4.1 Primary endpoint analysis**

#### **8.4.1.1 Safety/tolerability analysis**

Safety will be assessed through summaries of AEs, clinical laboratory tests, vital signs, and physical examination findings. All safety analyses will be based on the Safety population.

The incidence of AEs and SAEs will be tabulated by System Organ Class (SOC) and Preferred Term (PT), and by severity, relationship to treatment, and outcome. Tables of AEs leading to study drug discontinuation and withdrawal from the study will also be provided.

Adverse occurrences (as defined in Section 7.2) will be provided in a listing.

Descriptive statistics summarising local laboratory data will be presented by study visit. The change from baseline to each post-baseline visit and to the overall worst post-baseline value will also be summarised.

Descriptive statistics of vital signs will be presented by study visit, as well as the change from baseline at each study visit. The percentage of abnormalities in the physical examination will be presented by study visit.

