## 11 PROTOCOL VERSION HISTORY

Date	Version	Summary of changes
16 May 2022	1.0	–
24 May 2022	2.0	
 
• Addition of the definition of the end of the study
 
• Addition of adverse events of special interest
 
• Correction of the timeline for preparation of the clinical study report
 

11 July 2022	3.0	
 
• Deletion of Section 9.2 Biological sample and bacterial isolate retention
 

20 July 2022	4.0	
 
• Updated dose rationale in Section 1.4.3.
 
• Addition of the option in some circumstances that treatment with ceftobiprole may be stopped after 5 days at the discretion of the Investigator.
 
• Clarification that in Inclusion criterion 3, clinical criterion (i), references to hypotonia are to muscular or arterial hypotonia.
 
• Addition to Inclusion criterion 3 laboratory criterion (d), Interleukin-6 elevated according to local laboratory thresholds.
 
• Clarification that for the purposes of Exclusion criterion 4, the patient must have proven ventilator-associated pneumonia.
 
• Change of the duration of systemic antibacterial therapy within 7 days before start of study medication from 48 to 72 hours for the purposes of Exclusion criterion 12.
 
• Clarification that during the active treatment period, vital signs must be recorded within 30 minutes before the first study drug administration, and then three times daily.
 
• Section 7.2.7 has been amended to ensure that Special Situations are applicable to a patient population aged from <math>\geq 3</math> days to <math>\leq 3</math> months.
 
• Addition of two categories to the grading of the severity of adverse events.
 
• Section 7.4.2 has been amended to clarify the recording and reporting requirements for events occurring after execution of the study ICF but prior to dosing.
 

9 July 2024	5.0	
 
• Amendment of the planned study population to require at least eight patients, comprising at least two term neonates and six pre-term neonates.
 
• Reduction of the expected minimum treatment duration from 7 days to 3 days.
 
• Clarification of inclusion criterion 'hypotonia' by removing 'arterial' from inclusion criterion 3(i)
 

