## 1 INTRODUCTION

This document outlines the statistical methods to be implemented in the analysis of data collected within the scope of Basilea Pharmaceutica International Ltd., Allschwil, Protocol BPR-PIP-003 (A multicenter, open-label, single-arm, multiple-dose study to evaluate the safety, pharmacokinetics, and efficacy of ceftobiprole medocaril in term and pre-term neonates and infants up to 3 months of age with late-onset sepsis).

The purpose of this Statistical Analysis Plan (SAP) is to define the planned statistical methods in line with the study objectives. This plan should be read in conjunction with the study protocol (Version 5.0, dated 9 July 2024 at the time of finalization). All analyses will be conducted using SAS® Version 9.4 or higher.

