### **12 CHANGES IN THE PLANNED ANALYSIS**

There are no changes between the protocol-defined statistical analyses and those presented in this SAP.

The definition of the CE population has been clarified in this SAP. Patients should have received at least 48 hours of study drug to be included in the CE.

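### SAP 9.1.3 describes three AE severity grades where protocol 7.3.1 has five, so the severity table has no place for life-threatening or fatal events and no planned summary isolates non-fatal life-threatening AEs

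*SAP*

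**What the plan says.** Protocol 7.3.1 introduces its list with "The severity of an AE will be graded on the following scale" and gives five levels: Mild, Moderate, Severe, Life-threatening and Fatal. Severe is defined by major changes in age-appropriate behaviour and/or "non-life threatening changes in basal physiological processes". The version history, under version 4.0, records "Addition of two categories to the grading of the severity of adverse events".

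Protocol 8.4.1.1 sets out the primary safety analysis: "The incidence of AEs and SAEs will be tabulated by System Organ Class (SOC) and Preferred Term (PT), and by severity", as well as by relationship and outcome.

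SAP 9.1.3 states: "Severity of AEs is collected in the eCRF as 'Mild', 'Moderate', or 'Severe". It plans a table of AEs by severity, shows missing severity as Unknown and, for repeated occurrences of the same AE in one patient, says that "only the most severe will be counted".

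SAP 1 ties the plan to the current protocol: "This plan should be read in conjunction with the study protocol (Version 5.0, dated 9 July 2024 at the time of finalization". SAP 12 says: "There are no changes between the protocol-defined statistical analyses and those presented in this SAP".

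**The concern.** The two documents describe the same data item with different scales, and nothing in either reconciles them. Collapsing the top grades into Severe would not be neutral, because the physiological part of the protocol's definition of Severe excludes life-threatening changes. A life-threatening disturbance of oxygenation or perfusion therefore has no properly defined place on the SAP's scale. The rule of counting the most severe occurrence is likewise undefined for the two highest grades.

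Safety is the primary endpoint, and severity is one of the dimensions by which the protocol says AEs will be tabulated. At stake is whether a reader of the severity table can tell a severe event from a life-threatening one in a trial of neonates with sepsis.

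**Working it through.** The plan gives no figure to reproduce. The check compares the two scales and then looks through the SAP's planned AE outputs (sections 9.1 to 9.1.4, plus 8.2) for any that recovers the missing grades.

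| Protocol 7.3.1 grade | Row under SAP 9.1.3 | Other planned output that shows it |
|---|---|---|
| Mild | Yes | – |
| Moderate | Yes | – |
| Severe | Yes | – |
| Life-threatening | No | Included among SAEs (overview, SOC/PT table, listing), not separated from other SAEs |
| Fatal | No | AEs leading to death (overview rows and separate listing); Day 28 mortality table |

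**Count of grades.** Protocol 5, SAP 3, so 5 − 3 = 2 grades have no row. Adding the Unknown row, the SAP table has 3 + 1 = 4 categories. A table matching the protocol would have 5 + 1 = 6.

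**Fatal.** SAP 9.1 has overview rows for AEs leading to death and for study-drug-related AEs leading to death, and a separate listing. SAP 8.2 adds the Day 28 mortality table. Nothing essential about deaths is lost.

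**Non-fatal life-threatening.** Being life-threatening is one of the six seriousness criteria in protocol 7.2.2, so these events are SAEs. SAP 9.1 and 9.1.1 summarise SAEs as one group, with no split by criterion. The number of planned summaries that isolate these events is 0.

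**Weight of one patient.** The minimum numbers are eight overall, six pre-term and two term (SAP 3.1.2). SAP 4 calls for summaries by group and overall.

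- Overall: 1/8 = 12.5%
- Pre-term: 1/6 = 16.7%
- Term: 1/2 = 50%

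These are upper bounds if the minimum numbers are reached. Protocol 4.6 stops enrollment to each group at its minimum, so the actual numbers should be close to them.

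**Expected count.** The documents give no rate of non-fatal life-threatening AEs, so none is estimated. Protocol 7.4.3.1 keeps disease progression out of the AE data unless the outcome is death, which lowers the number.

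**Is the five-level scale intended?** Version 4.0 added two severity categories. The history does not name them, but the addition is consistent with three levels becoming five, and it predates the version 5.0 that the SAP cites. This is only supporting evidence: the conflict is between current protocol text and current SAP text.

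**The case against.** The strongest reply is that neither the eCRF nor the table shells are available. If the eCRF field has five levels, SAP 9.1.3 merely misdescribes it, and a table run on the collected data could show all five. That is possible, and it is why the field must be checked first. It does not remove the conflict: either the SAP describes the field wrongly, or the protocol's scale is not being collected.

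A second reply is that events in the top two grades need not be merged into Severe; they might be left ungraded and appear as Unknown. That also stands, since the SAP gives no mapping. In neither case would the table show the grade.

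A third reply concerns weight. Deaths are reported elsewhere, life-threatening events are in the SAE outputs, and with about eight patients each case can be read individually. This is largely right and limits the consequence. However, the SAP does not say that the listings show the seriousness criterion, and the protocol asks for tabulation by severity. The percentages above are also simply what one patient contributes to any row in this trial; they show scale and do not measure the defect itself.

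**Conclusion.** The concern holds. SAP 9.1.3 conflicts with protocol 7.3.1 and should be corrected before database lock. Two of five grades have no row in a table that belongs to the primary safety analysis, and non-fatal life-threatening AEs are not isolated in any planned summary. The practical effect is modest: one descriptive table, no hypothesis test, no decision rule, and fatal events visible elsewhere.

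The conflict in wording is certain from the text. The effect on the output assumes that the SAP is followed as written. Whether the fault lies in data collection or only in the SAP's description cannot be settled from these documents.

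**What to change.** Check the severity field in the eCRF first.

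- **If it has five levels:** amend SAP 9.1.3 and the table shell to the five protocol grades, and define the counting order as Fatal > Life-threatening > Severe > Moderate > Mild. The cost is SAP wording and one shell.
- **If it has three levels**, do one of the following:
  1. Correct the field and re-grade the affected AEs by query before database lock.
  2. Derive Fatal from the AE outcome, which protocol 7.4.3.1 requires on the AE page, and Life-threatening from the reason for seriousness, which protocol 7.4.3.2.1 requires on the SAE form. State the derivation in SAP 9.1.3 and declare it in SAP 12.

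Option 2 fills a severity grade from a seriousness criterion. It works only if the SAE form data are in, or can be reconciled with, the analysis database, so confirm that before choosing it. Option 1 costs a field correction and queries; option 2 costs a short derivation and a sentence in SAP 12. With about eight patients, either is a small task.
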